9.1.1.1.1 Inclusion Criteria for HCPs Prescribing/Dispensing or Informing on Oral Retinoid Therapy

HCPs will be included in this study if they meet the following criteria:

- Being a licensed medical specialist in one of the study countries who has prescribed oral retinoid therapies to WCBP (e.g., dermatologists, paediatricians, and/or general practitioners) at least once in the last 6 months (n=20 per country);
- Being a registered pharmacist in one of the study countries who dispensed oral retinoid therapy to WCBP at least once in the past 6 months (n=5 to 10 per country);
- Being a registered nurse providing education on PPP measures for oral retinoid therapies to WCBP, if applicable in the target country, at least once in the past 6 months (Poland, Spain, and France only (15); n= up to 5 for France, Poland, and Spain, not applicable for Germany);
- Willing to consent to participate in this study.

9.1.1.1.2 Exclusion Criteria for HCPs Prescribing/Dispensing Oral Retinoid Therapy

HCPs will be excluded from this study if meeting the following criteria:

- Being an inactive and retired HCP / allied HCP at the time of the interviews;
- Having a conflict of interest with the study (i.e., being employed by regulatory bodies, and/or pharmaceutical companies).

9.1.1.2 *Inclusion/Exclusion Criteria for WCBP (aged 18-49) and Parents, Guardians, or Caregivers of Adolescent WCBP*

9.1.1.2.1 *Inclusion Criteria for WCBP (aged 18-49) and Parents, Guardians, or Caregivers of Adolescent WCBP*

As shown in Table 2 below, between 25-28 WCBP and 10 parents, guardians or caregivers of adolescent WCBP per country (France, Germany, Poland, and Spain) will be targeted, if meeting the following inclusion criteria described below:

For isotretinoin (n=15 per country, 60 WCBP across all countries):

- Being female sex aged 18 to 49;
- Currently or recently (within the last 6 months) using isotretinoin;
- Willing/consent to participate in this study.

For acitretin (n=5 per country, 20 WCBP across all countries):

- Being female sex aged 18 to 49;
- Currently or recently (within the last 6 months) using acitretin*;
- Willing/consent to participate in this study.

For alitretinoin (n=5-8 from France, Germany, and Spain, 0 from Poland, 20 WCBP across all countries):

- Being female sex aged 18 to 49;
- Currently or recently (within the last 6 months) using alitretinoin*;
- Willing/consent to participate in this study.

Parent, guardians, or legal caregivers of Adolescent WCBP (n=10 per country)

- Parent, guardian or legal caregiver of adolescent WCBP aged 13 to 17 who are currently or recently (within the last 6 months) using isotretinoin or acitretin;
- Willing/consent to participate in this study.

Table 2. Target WCBP Samples across oral retinoid medication and country

Target country	Target WCBP samples to be recruited*			
	Isotretinoin	Alitretinoin (Min/Max)	Acitretin	Total (Min/Max)
France	15	5 - 8	5	25-28*

Germany	15	5 - 8	5	25-28*
Poland**	15	N/A**	5	20
Spain	15	5 - 8	5	25-28*
Total	60	20	20	100

*Note that this is a target number which may change depend on success of recruitment at local level. Country-specific targets may vary to account for the alitretinoin variability per country, but the overall sample will be of 100 WCBP globally.

Table 2 does not include n=10 parents, guardians, or caregivers of adolescent WCBP from each country.

**N/A: Not Applicable. Alitretinoin does not hold marketing authorisation in Poland. Thus, efforts will be made to recruit patients across France, Germany and Spain (between 5 and 8 per country), to ensure methodological robustness in interpreting results. A total of 20 WCBP taking or recently have taken alitretinoin will be recruited across all countries.

** Given the low prescription rates for these two retinoid treatments, the feasibility of identifying WCBP may be challenging. The following hierachal steps and sample boosting will be followed to achieve the sample population, and is described in detail in Appendix 2:*

1. Identify WCBP aged 18-49 using alitretinoin or acitretin (target 5 WCBP per country for acitretin and 5-8 WCBP in France, Germany, or Spain for alitretinoin);
2. If samples of WCBP per country cannot be enrolled, country-specific targets may be varied to account for an overall sample of 20 WCBP globally (representation per country included, while aiming to identify at least 5 WCBP using alitretinoin aged 35-49 globally);
3. Additional mitigation strategies that could be implemented includes targeting WCBP using alitretinoin or acitretin in the last 2 years or targeting an additional European country. This includes asking HCPs to provide information about this qualitative study to eligible WCBP for self-referral;
4. Identify WCBP aged 35-49 using isotretinoin with vignette descriptions of PPP measures for isotretinoin and/or acitretin;
5. Identify WCBP aged 18-49 using isotretinoin with vignette descriptions of PPP measures for isotretinoin and/or acitretin.

9.1.1.2.2 Exclusion Criteria WCBP (aged 18-49) and Parents, Guardians, or legal Caregivers of Adolescent WCBP

WCBP will be excluded from this study if they meet any of the following criteria:

Based on Template No.: RWI_TP_EPI0016
 Revision 1

Reference: RWI_WI_EPI0005

Effective Date: 15Jun2018

- WCBP does not have childbearing potential during the treatment course for oral retinoids (please see list of potential causes for losing childbearing potential in Appendix 1. List of potential causes for infertility in women);
- Unable to understand or comply to the study procedures, including the interview.

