The web-enabled audio conference semi-structured interviews are planned to be conducted in France, Germany, Poland, and Spain. Deidentified verbatim transcripts will be produced and translated into English. The verbatim transcripts will constitute the data and variable source for qualitative analyses.

Study Size:

The study population will include a sample, per country, of:

- 30 HCPs including 20 oral retinoid therapy prescribers (dermatologists, paediatricians, or general practitioners) and 10 dispensers and/or educators (pharmacists and/or nurses, if applicable in the targeted country about oral retinoid therapy PPP measures);
- 25 to 28 WCBP aged 18-49 per country, who currently or recently (in the past 6 months) used oral retinoid therapy, aiming with a distribution to represent:
 - 15 WCBP aged 18-49 using isotretinoin (n=60 across all countries),
 - 5 WCBP* aged 18-49 using acitretin (n=20 across all countries), and
 - 5-8 WCBP* aged 18-49 using alitretinoin in France, Germany, and Spain (n=20 across all countries);
- 10 parents, guardians, or caregivers of adolescent WCBP aged 13-17 currently or recently (in the past 6 months) used oral retinoid therapies, excluding alitretinoin.

** Given the low prescription rates for these two retinoid treatments, the feasibility of identifying WCBP may be challenging. The following hierachal steps and sampling boosting method will be followed to achieve the sample population, and is described in detail in Appendix 2:*

1. *Identify WCBP aged 18-49 using alitretinoin or acitretin (target 5 WCBP per country for acitretin and 5-8 WCBP in France, Germany, or Spain for alitretinoin);*
2. *If samples of WCBP per country cannot be enrolled, country-specific targets may be varied to account for an overall sample of 20 WCBP globally (representation per country included, while aiming to identify at least 5 WCBP using alitretinoin aged 35-49 globally);*
3. *Additional mitigation strategies that could be implemented includes targeting WCBP using alitretinoin or acitretin in the last 2 years or targeting an additional European country. This includes asking HCPs to provide information about this qualitative study to eligible WCBP for self-referral;*
4. *Identify WCBP aged 35-49 using isotretinoin with vignette descriptions of PPP measures for isotretinoin and/or acitretin;*
5. *Identify WCBP aged 18-49 using isotretinoin with vignette descriptions of PPP measures for isotretinoin and/or acitretin.*

Data Analysis:

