13.2 Appendix 2. Stepwise identification and sample boosting approach

To achieve methodological robustness in terms of the assessment of saturation of the insights reported during the interviews, a stepwise mitigation approach was developed for the recruitment and identification of participants using oral retinoids. This approach considers the following channels:

1. IQVIA's in-house Direct-to-Patient Recruitment channel
 - a. IQVIA's in-house Direct-to-Patient recruitment channel will assist with identifying WCBP
 - b. IQVIA's in-house recruitment channel will help identify WCBP and their parents for a study
 - c. Recruitment will be done through various sources such as patient and caregiver databases, social media, local patient associations, and direct clinician contact. The study will be promoted through diverse channels like email newsletters, recruitment flyers, and social media posts
 - d. Potential participants will be screened online or verbally via telephone. If eligible, they will be sent a link to an online informed consent
 - e. Once a participant qualifies and consents, IQVIA's in-house Direct-to-Patient Recruitment channel will collect their personal information and schedule an interview with IQVIA's Patient Centred Endpoints Research team
 - f. As an example for the activation of the next mitigation sample boosting approach, if the team are unable to identify 50% of the minimum alitretinoin sample after the fourth week of recruitment, then the team will move to step 2
2. Extended outreach for HCP-mediated referrals and other sources
 - a. As a contingency plan, recruitment through additional HCP referrals may be considered for certain countries
 - b. Additional HCPs and clinics will be contacted by IQVIA's in-house Direct-to-Patient Recruitment channel, who will provide them with recruitment materials to help identify potential participants
 - c. These HCPs will review screening information and share it with WCBP or their parents who may qualify for the study. Eligible WCBP who express interest in participating and who contact the recruitment team will self-refer to the study and receive a link to an online informed consent form and their preferred interview times will be noted if they agree to participate

- d. The involved HCPs will receive a fixed payment for their time, in line with fair market values; reconsideration of the amount for the fixed payments may be considered³. HCPs will not be paid per patient recruited.

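### The target of 25-28 adult WCBP per country is stated for Poland too, but Table 2 and the molecule targets give Poland 20

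*Protocol*

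**What the plan says.** The Abstract, under Study Size, plans "25 to 28 WCBP aged 18-49 per country" and makes no exception for Poland, although its own breakdown confines alitretinoin to France, Germany and Spain. Section 9.1.1.2.1 refers to Table 2 and targets "between 25-28 WCBP and 10 parents, guardians or caregivers of adolescent WCBP per country", naming Poland in the bracket that lists the four countries.

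The molecule criteria that follow in section 9.1.1.2.1 build the sample differently. Two molecules apply in all four countries: "For isotretinoin (n=15 per country, 60 WCBP across all countries") and "For acitretin (n=5 per country, 20 WCBP across all countries"). The third, alitretinoin, is set at 5-8 in each of France, Germany and Spain, none in Poland, and 20 overall. Table 2 accordingly gives Poland 20, gives the other three countries 25-28 each, and closes with 60, 20, 20 and 100. Its notes explain that alitretinoin has no marketing authorisation in Poland, fix alitretinoin at 20, and say that country targets may vary but "the overall sample will be of 100 WCBP globally".

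Three rules use these targets. Section 9.2.3.2 places the interim analysis at 50% of planned interviews, by country and molecule. Section 9.1.2.2.2 stops recruitment when the target is reached. Appendix 2 gives example triggers for moving through the sample-boosting steps, the first being that the team is "unable to identify 50% of the minimum alitretinoin sample after the fourth week of recruitment".

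**The concern.** A per-country sample size is stated in two places and contradicted by the table that one of them cites. The higher figure cannot be built for Poland: the only adult molecule targets there are 15 and 5, and nothing supplies the other 5 to 8 women.

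What is at stake is operational. The study has no power calculation. Its sample size works as a set of recruitment targets, a stopping point for recruitment and a denominator for the interim. Someone working from the Abstract would recruit 25-28 women in Poland, and someone working from Table 2 would recruit 20. The interim decides whether to add countries or enlarge the sample for a molecule, so its per-country denominator should not depend on which page is read.

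Appendix 2 has a separate looseness of the same kind. Its triggers for moving to steps 2, 3 and 4 are percentages of a minimum alitretinoin sample that is never given a number.

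**Working it through.** **Inputs.** Isotretinoin 15 per country in four countries; acitretin 5 per country in four countries; alitretinoin 5-8 in three countries and 0 in Poland, total 20 (section 9.1.1.2.1 and Table 2). Per country, 30 HCPs and 10 parents, guardians or caregivers (Abstract, Study Size). Interim at 50% (section 9.2.3.2). Triggers at 50% and 75% (Appendix 2).

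**1. The plan's own total.**
- Isotretinoin: 4 × 15 = 60.
- Acitretin: 4 × 5 = 20.
- Alitretinoin: fixed at 20. With 5-8 per country this is met by 5/7/8, 6/6/8 or 6/7/7 in some order.
- Sum: 60 + 20 + 20 = 100, as stated.

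**2. Poland.**
- From the molecule targets: 15 + 0 + 5 = 20, as in Table 2.
- From the text: 25-28.
- Overstatement: 25 − 20 = 5 to 28 − 20 = 8, which is 5/20 = 25% to 8/20 = 40%.

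**3. Total implied by the text.**
- 4 × 25 = 100 to 4 × 28 = 112.
- The lower end equals 100 only by coincidence. It would need 25 in Poland, where the molecule targets give 20. It would also need 25 in each of the other three countries, hence 25 − 15 − 5 = 5 alitretinoin users in each, or 15 in all instead of 20.

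**4. Interim point for Poland, all interviews counted.**

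| Polish adult WCBP | Planned interviews | 50% |
|---|---|---|
| 20 (Table 2) | 30 + 10 + 20 = 60 | 30 |
| 25 (text, low) | 30 + 10 + 25 = 65 | 32.5 |
| 28 (text, high) | 30 + 10 + 28 = 68 | 34 |

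**5. Appendix 2 triggers.** The minimum alitretinoin sample can be read as the sum of the country minima, 3 × 5 = 15, or as the fixed total, 20.

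| Reading of the minimum | 50% trigger | 75% trigger |
|---|---|---|
| 15 | 7.5 | 11.25 |
| 20 | 10 | 15 |

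Poland contributes nothing to either reading, so this ambiguity is independent of the Poland discrepancy.

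**The case against.** The strongest reply is that the protocol largely corrects itself. The sentence in section 9.1.1.2.1 defers to Table 2, the alitretinoin criterion excludes Poland, the table shows 20, and a note gives the reason. A recruiter who follows the molecule quotas has a single Polish target, 15 plus 5. That stands, and it is why the practical risk is low. It does not make the two sentences correct: one names Poland expressly, and the Abstract, which many people will read alone, has no table beside it. Nor does the note allowing country targets to vary cover the gap, because it ties that variation to alitretinoin, for which Poland has no target.

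It can also be said that the interim effect is slight. That is right. It is a few interviews at a milestone that the Abstract itself calls approximate, and within molecule the Polish adult cells are 15 and 5 throughout.

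Some stronger readings are tempting but unsupported:

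- A reader might add the Table 2 rows, get 3 × 25 + 20 = 95 to 3 × 28 + 20 = 104, and conclude that the total of 100 is wrong. It is not. The range 5-8 applies to each country under a fixed overall 20, the molecule totals sum to 100, and 100 lies inside 95-104. That three countries at their minimum would miss 20 is how a range under a fixed total behaves.
- A reader might put Poland's interim point at 10 against 12.5-14. That counts adult WCBP only, whereas the rule refers to all planned interviews.
- A reader might suppose that the Poland figure shifts the Appendix 2 triggers. Those depend on alitretinoin alone. They are also offered only as examples, and the 75% trigger opens country redistribution, not a change in eligibility.

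**Conclusion.** The point holds as a contradiction in a stated sample size. The Abstract and section 9.1.1.2.1 overstate the adult WCBP target for Poland by 5 to 8 women and imply 100-112 overall against a fixed 100. The consequence for the interim is 30 of 60 Polish interviews against 32.5-34 of 65-68, assuming that the per-country 50% counts HCPs and parents as well as adult WCBP. Recruitment in Poland would halt at 20 or at 25-28. No objective, molecule quota or overall total is affected, and the arithmetic of Table 2 is sound.

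The undefined minimum in Appendix 2 is real but secondary. It moves the 50% example trigger between 7.5 and 10 women and the 75% one between 11.25 and 15. The 50% trigger at week 16 is the one that opens the step where the recall window may be lengthened or a market added, and that step is discretionary.

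**What to change.** In the Abstract (Study Size) and in the opening sentence of section 9.1.1.2.1, state the adult target as: 25-28 in France, Germany and Spain; 20 in Poland; 100 in total (alitretinoin 20 across the three countries). The figures in Table 2 can stay as they are.

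In Appendix 2, replace the reference to a minimum alitretinoin sample with one number consistent with Table 2, and use it in every trigger expressed as a percentage.

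The alitretinoin figure should not be recast as a floor of at least 20. That would conflict with the fixed total of 20 and with the rule that recruitment halts at target.

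The cost is wording in two sections and one appendix. No participants are added.

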If this is not the case, triangulation of the qualitative findings related to barriers/challenges ranked by participants with existing literature (either peer-reviewed or from reports or assessments performed by institutional country agencies) identified following a narrative review of barriers to adhering to PPP measures highlighted by adult WCBP and parents, guardians or legal caregivers of adolescent WCBP in the Nordic/northern European regions will be performed. The triangulation will seek to confirm if the diversity of the qualitative findings collected is able to cover known barriers and challenges to adhering to PPP measures previously identified in northern European countries.

If the most important barriers identified compare across all included countries, no additional country will be included for the subsequent portion of the study. If this is not the case, a recruitment strategy including samples representative from other European regions (e.g. Nordic countries) will need to be considered. Additional details are presented in the Qualitative Analysis Plan (Annex 4. Qualitative Analysis Plan). The decision-making plan for assessing if the study data is representative of the diversity of barriers/challenges reported across European regions, including northern Europe, is presented in **Figure 3**.

Figure 3. Decision flow for conclusions on the representativeness of the diversity of barriers/challenges reported across European regions

Similarly, to assess the consistency of barriers and challenges to adherence between the three oral retinoid molecules (isotretinoin, acitretin, and alitretinoin) used by adult WCBP and two oral retinoid molecules used by adolescent WCBP (isotretinoin and acitretin), code

Based on Template No.: RWI_TP_EPI0016
 Revision 1

Reference: RWI_WI_EPI0005

Effective Date: 15Jun2018

saturation between molecules will be assessed and compared. The interim analysis will involve the coding of the transcripts and assessment of code saturation and code meaning, as described in section 9.2.3.1. Reviewing the frequency and consistency of codes to determine if new codes continue to emerge or if the existing codes sufficiently capture the data will determine whether additional samples for specific molecules (e.g. acitretin) will need to be increased to achieve code saturation per molecule. Additional details are presented in the Qualitative Analysis Plan (Annex 4. Qualitative Analysis Plan).

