- e. Other recruitment channels, including social media and patient advocacy groups may be extended and further considered.
- f. As an example for the activation of the next mitigation sample boosting approach, if the team are unable to identify 50% of the alitretinoin minimum sample by the 16th week of recruitment, the team will move onto step three.

3. Extension of the study's inclusion criteria or extension of study to other market³
 - a. An extension of the criterion for having used oral retinoids in the last 6 months may be extended to 12 months (or up to 24 months).
 - b. Extension of the study to other markets where oral retinoids are marketed may be considered
 - c. As an example for the activation of the next mitigation sample boosting approach, if the team are unable to identify 75% of the alitretinoin minimum sample by the 12th week of recruitment, the team will move onto step four.
4. Country re-distribution³
 - a. Country-specific WCBP samples may be redistributed to the other countries under study, depending on the feasibility of identifying and recruiting patients using alitretinoin.
 - b. As an example for the activation of the next mitigation sample boosting approach, if after six months following the start of the recruitment the overall alitretinoin sample is not achieved, the team will implement step five.
5. Clinical vignettes (specific to alitretinoin)
 - a. Hypothetical perceptions of the PPP measures for alitretinoin will be explored based on isotretinoin vignette descriptions of PPP measures.
 - i. Their hypothetical views on the Pregnancy Prevention Programme (PPP) measures for alitretinoin will then be investigated using scenario-based descriptions of these measures.

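### Vignette interviews with isotretinoin users may fill places meant for alitretinoin and acitretin users, and the protocol contradicts itself on which drug the vignettes describe

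*Protocol*

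**What the plan says.** Section 9.1.1.2.1 defines the three adult strata by drug actually used, currently or within the last 6 months: "For isotretinoin (n=15 per country, 60 WCBP across all countries"), "For acitretin (n=5 per country, 20 WCBP across all countries") and "For alitretinoin (n=5-8 from France, Germany, and Spain, 0 from Poland, 20 WCBP across all countries"). The notes to Table 2 add that "the overall sample will be of 100 WCBP globally", and that the alitretinoin total of 20 is made up of women who take or recently took that drug.

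For the two low-use drugs, the same section and the Abstract give a five-step fallback: "The following hierachal steps and sample boosting will be followed to achieve the sample population". Steps 1 to 3 still look for users of the drug in question. Step 4 does not: "Identify WCBP aged 35-49 using isotretinoin with vignette descriptions of PPP measures for isotretinoin and/or acitretin". Step 5 repeats step 4 for ages 18-49.

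Both places refer to Appendix 2 for the detail. There, step 5 limits clinical vignettes to alitretinoin and says: "Hypothetical perceptions of the PPP measures for alitretinoin will be explored based on isotretinoin vignette descriptions of PPP measures". A sub-item adds that views on the alitretinoin measures will be explored through scenario descriptions of those measures.

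Section 9.2.3.2 examines whether barriers are consistent across the three molecules; code "saturation between molecules will be assessed and compared", and the result decides whether a molecule needs more interviews. Section 9.2.2.2 later groups barriers by specific oral retinoid to support targeted actions.

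**The concern.** There are two linked problems.

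First, the strata are defined by use of the drug, but steps 4 and 5 reach the sample with women who need never have used it. The protocol text does not cap these interviews, label them as a separate group, or say that they stay outside the target of 20. Appendix 2 opens by giving saturation assessment as the reason for the stepwise approach, which points towards counting them.

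Second, the two descriptions of the vignettes conflict. A team following section 9.1.1.2.1 would never present alitretinoin. A team following Appendix 2 would never use a vignette for acitretin.

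What is at stake is the answer by molecule. An isotretinoin user lacks the alitretinoin user's condition, care pathway and experience of the drug. If she is counted as alitretinoin, that stratum partly repeats isotretinoin codes. The codebook then looks stable sooner and the molecules look more alike than they may be.

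**Working it through.** **Step 1. Reproduce the sample size (Table 2).** Isotretinoin 15 × 4 = 60. Acitretin 5 × 4 = 20. Alitretinoin 5 to 8 in each of three countries, 15 to 24, fixed at 20. Total 60 + 20 + 20 = 100, as stated. That 100 therefore consists of users of the named drug in every cell.

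**Step 2. Set the vignette rules side by side.**

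| | Section 9.1.1.2.1 and Abstract, steps 4-5 | Appendix 2, step 5 |
|---|---|---|
| Stratum to be filled | alitretinoin or acitretin | alitretinoin only |
| Vignette content | isotretinoin and/or acitretin | isotretinoin descriptions; sub-item: alitretinoin measures |
| Alitretinoin vignette | not named | yes, by the sub-item |
| Acitretin vignette | allowed | no route |
| Timing | none given | example trigger six months after recruitment starts |
| Cap on number | none | none |

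**Step 3. Compare the current rows of Table 1.**

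| | Isotretinoin | Alitretinoin | Acitretin |
|---|---|---|---|
| Contraception before / during / after | 1 month / yes / 1 month | 1 month / yes / 1 month | 1 month / yes / 3 years |
| Pregnancy test before / during / after | yes / ideally monthly / 1 month | yes / ideally monthly / 1 month | yes / ideally monthly / 3 years |
| Checklist, form, card | yes, yes, yes | yes, yes, yes | yes, yes, yes |
| Supply | ideally 30 days | ideally 30 days | ideally 30 days |

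Alitretinoin and isotretinoin agree in every column. Acitretin differs in the two post-treatment columns. So for alitretinoin a vignette adds nothing to the listed measures an isotretinoin user already knows, whichever of the two drugs it names. For acitretin it can present something new.

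**Step 4. Size, as an illustration.** The number of substitutes s is not given, so a range is needed. If 15 actual alitretinoin users are found (the Table 2 minimum), s = 5 and 5/20 = 25%. If 8 are found (just over half of that minimum, 0.5 × 15 = 7.5), s = 12 and 12/20 = 60%.

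Assume the substitutes are pooled and answer as isotretinoin users do. A true difference between molecules then appears at 1 − s/20 of its size: 75% for s = 5 and 40% for s = 12.

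Assume also that a barrier specific to the molecule is held by a proportion p of its actual users. The chance of hearing it at least once is 1 − (1 − p)^(20 − s):

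| Actual users | p = 10% | p = 15% |
|---|---|---|
| 20 | 88% | 96% |
| 15 | 79% | 91% |
| 10 | 65% | 80% |
| 5 | 41% | 56% |

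A genuine shortfall gives the same loss. The difference is that a stratum reported as 20 would hide it.

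**Step 5. Timing.** Data collection starts May to August 2025 (section 6), taken here as a proxy for the start of recruitment. Adding six months gives November 2025 to February 2026. The interim analysis is planned for October to December 2025 and data collection ends April to July 2026. On Appendix 2's example trigger, vignette interviews would largely come after the interim comparison and before the final one. Steps 4 and 5 of the body text carry no timing, so earlier use is not ruled out.

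**The case against.** The strongest reply is that the Qualitative Analysis Plan, to which sections 9.2.3.1 and 9.2.3.2 refer for saturation by molecule, is not shown and may keep vignette interviews apart. That stands as a limit on the bias argument: pooling is a possibility, not a stated rule. It does not remove the point, because who fills a stratum and what the vignettes describe are set in the protocol, and set inconsistently.

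A reader might infer that the report will present 20 alitretinoin users who never took the drug. The documents do not support that. Section 9.1.1.2.1 keeps use of the drug as the inclusion criterion, section 9.1.2.2.2 asks for proof of eligibility, and Appendix 2 calls the vignette views hypothetical.

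A reader might also infer that the vignettes always name the wrong drug. That is too strong. For acitretin, an acitretin vignette names the right drug and only the isotretinoin option is wrong. For alitretinoin, the sub-item in Appendix 2 does describe the alitretinoin measures, and the body wording may be a slip.

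The direction of bias is also open to question for acitretin, since its 3-year post-treatment measures could prompt new codes. This is fair, so the argument from identical measures is confined to alitretinoin.

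Finally, naming alitretinoin in steps 4 and 5 would not by itself help, given Table 1. That is correct, and is why separating these interviews matters more than renaming the vignette.

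**Conclusion.** The point holds as a contradiction in the protocol with a conditional consequence. Steps 4 and 5 use isotretinoin users to reach a sample that is defined by use of another drug, and the body text and Appendix 2 cannot both be followed on the vignettes. For alitretinoin, counting these interviews would push saturation and the between-molecule comparison towards saturated and consistent. For acitretin the concern rests on the body text alone.

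The consequence needs two things: that the last-resort step is activated, and that the interviews are pooled. The 25% to 60% range illustrates 5 to 12 substitutes of 20; no document forecasts a shortfall. It would go too far to conclude that the interim decision is compromised, since on Appendix 2's example timing the effect would fall mainly on the final comparison. The rating is should-fix: confidence is high in the contradiction, lower in the size of any bias.

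**What to change.** - State in section 9.1.1.2.1, the Abstract and Appendix 2 that vignette interviews with isotretinoin users do not count towards the acitretin or alitretinoin 20, towards saturation for those molecules, or in the between-molecule comparison. Carry the same rule into the Qualitative Analysis Plan.
- Report these interviews as a separate hypothetical group, and give the number of actual users reached for each molecule beside the target.
- Reconcile steps 4 and 5 with Appendix 2 on which molecule the vignettes describe, and on whether there is a vignette route for acitretin.

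The cost is wording only. The downside is that the reported number of actual alitretinoin or acitretin users may be below 20, but the report would then show the shortfall openly.
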